The results of the largest study conducted thus far on the antidepressant effects of repeated ketamine infusions included twenty-four subjects with TRD who underwent a washout of antidepressant medication followed by a series of up to six intravenous (IV) infusions of ketamine (0.5 mg/kg) over 40 minutes administered open-label three times weekly over a 12- day period (Murrough et al., 2013b). The TRD patients meeting response criteria were monitored for depressive relapse for up to 83 days from the last infusion. The antidepressant effect of ketamine was evident very early in the course of treatment. Moreover, ketamine exerted a broad-spectrum effect on individual symptoms of depression, and rapid response to the first infusion was highly predictive of a sustained response to subsequent infusions (Murrough et al., 2013b). Although preliminary, ketamine's large and sustained effect size regarding its antidepressant properties seems to be carried over repetitive IV infusions. In particular, suicidal ideation (SI) rapidly decreases even among non-responders to repetitive ketamine IV infusions. Therefore, ketamine is suggested to exert a unique anti-SI effect even in the absence of a full antidepressant response (Murrough et al., 2013b). This finding is consistent with previous reports highlighting the potential anti-SI effects of single dose infusion of IV ketamine in depressed populations (Diaz-Granados et al., 2010b; Larkin and Beautrais, et al 2011; Price et al., 2009).

Recently, researchers at the Mayo Clinic have performed serial ketamine infusion but at a lower infusion rate (Rasmussen et al., 2013). Ten depressed patients were treated with twice weekly

infusions of ketamine 0.3 mg/kg administered over 100 min until either remission was achieved or four infusions were given. Patients were naturalistically followed weekly for four weeks after completion of the infusions and psychiatric side effects were assessed with the Young Mania Rating Scale (YMRS; Young et al., 1978) and the Brief Psychiatric Rating Scale (BPRS; Overall and Gorman, 1988) respectively. While a 50% remission rate was documented without any significant increase on BPRS or YMRS measures, only two patients maintained remission at the 4-week follow up session. Nonetheless, it seems that ketamine infusions at a lower rate than previously reported might produce similar efficacy, excellent tolerability, and thus may be more available for routine clinical care.

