The BAC-A is based on the Brief Assessment of Cognition in Schizophrenia (BAC-S). The BAC-S has been validated both linguistically and psychometrically in a number of psychiatric populations, including patients with schizophrenia and BD (Cuesta et al., 2011; Hill et al., 2013; Kuswanto, Sum, & Sim, 2013; Salgado et al., 2007; Segarra et al., 2011). It has been shown to be as valid and sensitive as a traditional neuropsychological assessment and takes approximately 35 minutes to administer (Keefe et al., 2004; Velligan et al., 2004). Six of the 8 subtests of the BAC-A match those found in the BAC-S. These tests are the Token Motor Task, Symbol Coding, List Learning, Digit Sequencing Task, Category Instances (Animals) and

Controlled Oral Word Association Test (F and S-words), Tower of London (Keefe et al., 2004). In addition to these 6 subtests the BAC-A comprises the Emotion Inhibition Test (a modified version of the Emotional Stroop task (LaMonica, Keefe, Harvey, Gold, & Goldberg, 2010; Williams, Mathews, & MacLeod, 1996)) and the affective auditory verbal learning test (Affective interference test). The latter task is similar to the Affective Auditory Verbal Learning Test (AAVLT) (Snyder & Harrison, 1997). Assessments will be conducted prior to the treatment period, 4, and 8 weeks into the treatment. To avoid potential learning bias we will use parallel versions of the word lists for the Emotion Inhibition Test, Tower of London, and the Verbal Memory Tests to assess cognitive changes over the course of the ketamine treatment.

Study design

We will follow an AB design and clinical/cognitive assessments will be taken at baseline, week 4, week 8, and week 12. Given the preliminary nature of this treatment study this open label trial aims to generate an effect size for a subsequent RCT and/or future grant application. No *a priori* estimates of the power/effect size were therefore calculated.

Timeline	After Each Infusion	Baseline	Week 4	Week 8	Weekly Follow-up Phone Calls	Week 12
SCID-I		X				
Clinical scales (MADRS, CGI, YMRS)		X	X	X	X	X
PANAS, Q-LES-Q, self-report	X					
BAC-A		X	X	X		X
Blood tests/Sample		X	X	X		X
Urine drug test	X	X				

Study sample

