- 12) Pregnancy or Breast feeding. All female in reproductive age will undergo pregnancy tests. Female participants will be required to provide evidence of use of contraceptives during the course of the study.
- 13) Unable to understand the design and requirements of the study
- 14) Unable to sign the informed consent for any reason
- 15) An assigned responsible adult has provided assent to assist in patient's study participation. The responsible adult agrees to be present at each study appointment as well as provide transportation to study appointments for the patient.

Non responders

If a patient does not respond to the study treatment by their 4th treatment they will be removed from the study due to non-response. A successful response to study treatment will be at least a 30% reduction in MADRS scores from screening until the 4th treatment. Again if a patient does not respond by the 4th treatment, they will be excluded from the study.

Unanticipated Hospitalizations

If a patient needs to be hospitalized for worsening of symptoms or for their own personal safety, they will be removed from their study participation and their study treatment will end at that time.

Feasibility

Subject recruitment: Our center has access to a large patient pool (drawing from a metropolitan area of about 5.5 million people) and well-established ability to recruit patients with mood disorders. [name] is the department chair for Psychiatry and Behavioral Sciences and Director of the University of Texas, Center of Excellence on Mood Disorders. He successfully completed a large number of studies over the past 20 years with excellent recruitment of MDD and BD subjects at this site. We will also recruit participants through doctor referrals. Participants will be exclusively outpatients.

Funding of the study: given the preliminary nature of this study we plan to use departmental funding for the current study and then possibly apply for a larger grant later on once we have collected preliminary data and calculated optimal power/effect sizes for ketamine treatment in individuals with TRD.

Data analysis

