Normality assumptions for continuous variables will be examined. Where appropriate, outliers will be winsorised and log, square root or reciprocal transformations applied to achieve normality if appropriate. If normality cannot not been achieved, either untransformed or dichotomized scores were used. Baseline characteristics will be compared between responders and non-responders with the Mann-Whitney U test for continuous variables and the chi-square test for categorical variables. Changes between two time-points for continuous variables were tested with paired t tests, and associations between continuous variables will be quantified with the Spearman correlation coefficient. Random effects models will be performed to quantify changes in clinical score and its component items over time and to compare temporal differences between eventual responders and non-responders. Splines will be used to determine differences in the pattern of response over time among all patients and to identify the time at which there was no additional improvement in depressive symptoms. Additionally, the relationship between response status between baseline and end of study calculating sensitivity, specificity, and positive and negative predictive values will be reported. Time to relapse for patients who met response criteria at end point will be estimated with the Kaplan-Meier method. Analyses will be performed with IBM SPSS Statistics (version 19; SPSS, Chicago, Illinois) and SAS (version 9.2; SAS, Cary, North Carolina).

Study timetable

Activities	Months											
	1	2	3	4	5	6	7	8	9	10	11	12
Obtain IRB approval at UTHealth and HCPC		x	x									
Set up the Ketamine Ambulatory Clinic at HCPC			x	x								
Start recruiting patients and collecting data					x	x	x	x				
Analyses of initial dataset								x	x	x		
Submit a poster to International meeting with final results									x	x	x	
Submit result to high-impact peer-reviewed journals											x	x

Importance of the knowledge to be gained

Our findings will enhance our understanding of the safety, tolerability and efficacy of ketamine infusion in adults with TRD. Further it will help us understand the feasibility of this treatment in a psychiatric setting. The findings of the present study will also constitute an important foundation for future grant proposals investigating the efficacy of this intervention as a measure of suicide prevention.

*Women and Minority Inclusion in Clinical Research**Inclusion of Women*

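### If the clinical score is MADRS, comparing its course by response group is circular; and if 4th-treatment response is the early index, removal leaves only the PPV estimable

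*Combined protocol and SAP*

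**What the plan says.** The trial is a single-arm, open-label study of 30 patients whose primary outcome is remission judged on MADRS. Four parts of the protocol bear on this point.

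- **Trajectories (Data analysis).** "Random effects models will be performed to quantify changes in clinical score and its component items over time", and the same models are to "compare temporal differences between eventual responders and non-responders". The score is not named. The next sentence plans splines to "identify the time at which there was no additional improvement in depressive symptoms".
- **Accuracy (Data analysis).** The relationship of "response status between baseline and end of study calculating sensitivity, specificity, and positive and negative predictive values" is to be reported. No early index is named. End-point response criteria are mentioned for the Kaplan-Meier analysis, but no cut, reference visit or time point is given.
- **Removal (Non responders).** "A successful response to study treatment will be at least a 30% reduction in MADRS scores from screening until the 4th treatment". The consequence is also stated: "If a patient does not respond to the study treatment by their 4th treatment they will be removed from the study due to non-response". A separate paragraph, Unanticipated Hospitalizations, removes patients who need admission.
- **Schedule (C. Approach; Study design timeline).** MADRS, CGI and YMRS are taken at baseline, weeks 4, 8 and 12, and at the weekly follow-up calls. No MADRS is listed at the 4th treatment.

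**The concern.** Sorting patients by how far MADRS fell and then testing whether MADRS fell differently in the two groups gives a difference by construction. A small p-value or a narrow interval could be taken as a finding about how responders improve, when the labelling alone can produce it.

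The accuracy table raises a related problem. If early response means response at the 4th treatment, everyone without it leaves the study, so nobody remains who could show that an early non-responder responds later. The background section cites an earlier series in which "rapid response to the first infusion was highly predictive of a sustained response to subsequent infusions". A sensitivity or NPV of 100% produced by the removal rule would look like confirmation of that. The study is meant to supply estimates for a later randomised trial or grant, so such figures may be carried forward.

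**Working it through.** The plan gives no power, alpha or effect-size figure, so there is nothing of its own to reproduce. Simulation inputs below are assumptions unless a source is given.

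**1. When removal happens.** Infusions are twice weekly for the first 4 weeks, so the 4th treatment falls at 4 / 2 = about week 2. The first scheduled on-treatment MADRS is at week 4. A patient removed for non-response therefore has baseline and no scheduled on-treatment value. At best there is the unscheduled score that the removal rule itself needs.

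**2. Circularity, first simulation.** Inputs: n = 30 (protocol); mean MADRS 32, 20, 20 at weeks 0, 4, 8; SD 6; within-patient correlation 0.5; two-sided 0.05. All patients come from one population, so there is no true responder class. Label: responder if (week 0 − week 8) / week 0 ≥ 0.50. Test: likelihood ratio for group-by-time in a random-intercept model with categorical time.
- Labels from the outcome: significant in 95.9% of 294 usable runs.
- Labels permuted: 6.1% of 297.
- Mean difference in week-8 change between the labelled groups: 9.1 points, all of it from labelling.

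A companion grid used t tests on change (cut 30% or 50%, SD 4–8, correlation 0.2–0.8). The week-8 comparison was significant in 82–100% of usable runs. The week-4 comparison, at a visit not used for labelling, was significant in 13–42%, because both changes share the same baseline.

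**3. Circularity, wider grid.** Baseline 32; common drop 35, 45 or 55%; week-8 cut 30% or 50%; between/residual SD 4/7, 4/5 or 6.7/4.4, giving correlations 16/65 = 0.25, 16/41 = 0.39 and 44.9/64.3 = 0.70. There were 1,000 trials in each of 36 settings. Usable means at least 2 patients per group (53–100% of runs).

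| Group-by-time p < 0.05, categorical time | Share of usable runs |
|---|---|
| Weeks 0/4/8, all followed | 86–100% |
| Remaining patients only | 85–100% in five of six drop/cut pairs; 68–88% in the sixth (35% drop, 50% cut) |
| Removed kept as non-responders | 75–100% |
| Weekly calls and week 12 added, all followed | 67–99% |
| Weekly calls and week 12 added, after removal | 46–93% |
| Permuted labels | 3–7% |
| A scale unrelated to MADRS | 3–6% |

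With linear time the result depends on the model: 8–100% over the treatment period and 2–39% to week 12. Baseline MADRS compared by group (Mann-Whitney) was significant in 3–60%.

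**4. Accuracy table if the index is 4th-treatment response.** This is algebra and needs no simulation. As an assumed example, 18 of 30 continue and 13 of those respond at the end; had the 12 removed patients been followed, 3 would have responded later.

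| | All followed (hypothetical) | Remaining only | Removed = non-responders |
|---|---|---|---|
| TP, FP, FN, TN | 13, 5, 3, 9 | 13, 5, 0, 0 | 13, 5, 0, 12 |
| Sensitivity TP/(TP+FN) | 13/16 = 0.81 | 13/13 = 1 | 13/13 = 1 |
| Specificity TN/(TN+FP) | 9/14 = 0.64 | 0/5 = 0 | 12/17 = 0.71 |
| NPV TN/(TN+FN) | 9/12 = 0.75 | 0/0 | 12/12 = 1 |
| PPV TP/(TP+FP) | 13/18 = 0.72 | 13/18 = 0.72 | 13/18 = 0.72 |

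PPV uses continued patients only and is the same in all three columns (exact 95% interval 0.47–0.90). In the last column specificity depends on the imputation; other assumed splits gave 0.33–0.86.

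**5. Response-rate denominator.** In the wider grid the rate over all treated patients was 5–29 points below the rate among remaining patients: for example 66.9% against 38.3% (28.6 points), 48.4% against 34.5% (13.9) and 66.7% against 61.6% (5.1).

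**The case against.** The strongest reply is that the circularity rests on several conditions. The score must be MADRS, end-point response must be MADRS-based, and a group-by-time test or interval must be reported. The plan names no such test, and comparing timing may mean no more than plotting when the curves separate, which is legitimate. No hypothesis compares responders with non-responders, and the study is preliminary. All of this stands as a limit on the point. It does not remove it: the plan says the groups will be compared by model and does not restrict that to description.

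A second reply is that the simulated labels use week-8 change, whereas the only documented rule applies at the 4th treatment. That is fair. Under the documented rule the difficulty changes form: non-responders leave with almost no course to model.

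A reader might also infer more than the documents support:
- That the plan takes 4th-treatment response as its index. It names none. Response after the first infusion is another candidate and does not make the table degenerate automatically, although removed patients would still lack an observed end-of-study status.
- That all the predictive values are fixed by removal. PPV is not, and specificity is 0 or depends on the imputation.
- That every scale is affected. Scales that do not define response, such as YMRS, are not circular in this direct way.
- That 30% is the end-point response cut. The protocol gives it only as the rule at the 4th treatment.

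**Conclusion.** The concern holds in limited form. On the natural reading that the clinical score is MADRS, a categorical group-by-time test or interval by eventual response is largely built in: about 86–100% significant with everyone followed and no true difference, and lower in some settings with removal or the follow-up calls. These rates rest on assumed means, SDs, correlations and cuts, and on usable runs only. They show the mechanism and do not forecast this trial's result. No general claim is made for linear-time models.

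The undefined index and end-point response are firm findings. The degenerate table is conditional on a 4th-treatment index but, given that, follows exactly. It might be inferred that the main result is compromised; it is not, since these are secondary analyses and the circularity does not touch remission. The change should be made before analysis.

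**What to change.** 1. State which scale the clinical score is. Present MADRS and item trajectories by eventual response as description only, with no group-by-time test, interval or inferential claim. Report baseline MADRS by group without a test as well.
2. Before analysis, name the early index and define end-point response by its cut, reference visit and time point. If the index is 4th-treatment response, report only PPV, labelled as conditional on continuing, and omit sensitivity, specificity and NPV.
3. Report the response rate with all treated patients as denominator, counting patients removed for non-response as non-responders and showing those removed for hospitalisation separately. Give the rate among continued patients alongside it.
4. Reconcile the Non responders section, which relies on a MADRS score at the 4th treatment, with the schedule in C. Approach and the Study design timeline. No view is taken here on the continuation rule.

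Items 1–3 cost analysis-plan wording and minor programming, with no new visits. The price is a lower headline response rate and, under a 4th-treatment index, the loss of most of the accuracy table.
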